#### **6.7. Scanning Session 2 Follow-up**

1. Call participant and check on any adverse events that may have occurred following the scanning session.

#### **6.8. AUD Follow-up**

1. For AUD participants: Participants will be contacted 30, 60, & 90 days following the final scan to assess levels of social support, drinking and well-being (see section 6.11).

#### **6.9. Participant Compensation**

Participants will be paid \$50 for completing the initial survey battery at intake and up to \$5 more depending on how well they do on one of the tasks. Participants will receive \$100 for each fMRI scan and up to \$40 more per scan depending on how well they perform the MID task. If participants complete both scans the total compensation will be between \$250 and \$335. The AUD group can earn an additional \$5 for completing the 30-day follow-up, \$10 for the 60-day follow-up, and \$15 for the 90-day follow-up. Compensation will be provided in the form of cash or gift cards. Participants will be paid after the completion of each scan. If for some unforeseen reason any of the sessions are cut short or run longer than anticipated, participants will be paid a prorated amount for the session (\$20/hour). Reasonable local transportation costs will be reimbursed. Participants can also request to receive a black and white printed picture of their brain obtained by MRI when they come in for their second fMRI visit.

### 6.10. Schedule of Activities

Protocol Activity	Screening	Intake	Scanning Session 1	Scanning Session 1 Follow-up	Scanning Session 2	Scanning Session 2 Follow-up
Visit # / Phone call	Phone call	1	2	Phone call	3	Phone call
Screening Questionnaire	X					
Informed Consent		X				
M.I.N.I. Interview		X				
Intake Questionnaires		X				
Intake Tasks		X				
Urine Drug, Ethanol, & Pregnancy Screen		X	X		X	
Syntocinon® or Placebo Administration			X		X	
Scanning Questionnaires			X		X	
fMRI Scanning: Anatomical			X		X	
fMRI Scanning: Tasks			X		X	
Obtain Saliva Samples		X	X		X	
Monitor Heart Rate and Blood Pressure			X		X	
Adverse Event Recording			X	X	X	X

\*AUD participants will also be contacted 30,60, & 90 days following their final scan and asked to complete several questionnaires (see section 6.11).

## 6.11. List of Questionnaires & Surveys

### *Intake*

#### Mood/Anxiety

- Patient Health Questionnaire (PHQ-9, v3) (2-3 minutes)
- Adverse Childhood Experiences (ACE, v3) (5 minutes)

#### Personality & Personal History

- NEO-Personality FFI (NEO-FFI, v3) (15 minutes)
- General History (v3) & Women's Health (WHQ, v4) Questionnaires (4 minutes)
- Drug History (v4) and Alcohol Use (AUQ, v4) Questionnaires (5 minutes)
- Readiness Ruler (v2, 1 minute)
- Alcohol Use Disorders Identification Test (AUDIT, v4) (5 minutes)
- Fagerstrom Test (v2, 3 minutes)
- Autism Spectrum Quotient (AQ-10, v3) (5 minutes)

#### Social and Well Being Measures

- Important People/Social Relationships Index (SRI-IPI, v6) (15-20 minutes)
- MOS Social Support Survey (MOS-SS v3) (1-2 minutes)
- Social Value Orientation (SVO, v3) (5 minutes)
- Emotional Contagion (EC, v4) (5 minutes)
- Anticipatory & Consummatory Interpersonal Pleasure Scale (ACIPS, v3) (7 minutes)
- Dysfunctional Attitudes Scale (DAS-A, v5) (10 minutes)
- Brief Fear of Negative Evaluation (BFNE-II, v3) (5 minutes)
- Interpersonal Reactivity Index (Brief IRI, v3) (5 minutes)
- Toronto Alexithymia Scale (TAS-20, v2) (7 minutes)

### *Scanning*

- Positive and Negative Affect Schedule (PANAS, v3) (5 minutes)
- Inclusion of Other in the Self scale (iOS, v2) (1-2 minutes)
- UCLA Loneliness Scale (UCLA-LS, v3) (2-5 minutes)
- Scanning VAS Scales (v3, 2-3 minutes)
- Drug Effects Questionnaire (DEQ, v3) (3 minutes)

### *Follow-up (30, 60, 90 days)*

- Satisfaction with Life Scale (SWLS, v4) (1-2 minutes)
- Follow-up VAS Scales (v2, 1-2 minutes)
- MOS Social Support Survey (MOS-SS, v3) (1-2 minutes)
- Timeline Followback/Quick Drinking Screen (QDS, v2) (3 minutes)

## 7. ADVERSE EVENT REPORTING

### Adverse Event Definition

An adverse event (AE) is any untoward medical occurrence in a subject participating in an investigational study or protocol regardless of causality assessment. An adverse event can be an unfavorable and unintended sign (including an abnormal laboratory finding), symptom, syndrome or disease associated with or occurring during the use of an investigational product whether or not considered related to the investigational product.

#### These events may be:

- a. *Definitely related*: clearly associated with study drug/treatment
- b. *Probably related*: likely associated with study drug/treatment
- c. *Possibly related*: may be associated with study drug or other treatment
- d. *Unlikely to be related*, or
- e. *Definitely not related* to the study drug/treatment

*For reporting purposes, an AE should be regarded as definitely or probably related to the regimen if the investigator believes that at least one of following criteria are met:*

- a. There is a clinically plausible time sequence between onset of the AE and the administration of the study drug or treatment.
- b. There is a biologically plausible mechanism for the study drug or treatment causing or contributing to the AE.
- c. The AE cannot be attributed solely to concurrent/underlying illness, other drugs, or procedures.
- d. A potential alternative cause does not exist.

**Serious Adverse Events (SAE):** An adverse drug experience occurring at any dose that results in any of the following outcomes:

- a. Death
- b. A life-threatening adverse drug experience
- c. Inpatient hospitalization or prolongation of existing hospitalization
- d. A persistent or significant disability &/or incapacity
- e. A congenital anomaly or birth defect

Important medical events that may not result in death, be life-threatening, or require hospitalization may be considered a serious adverse drug experience when, based upon appropriate medical judgment, they may jeopardize the patient or subject and may require medical or surgical intervention to prevent one of the outcomes listed in this definition. A serious adverse experience includes any experience that is fatal or immediately life threatening, results in a persistent or significant disability/incapacity, requires or prolongs in-patient hospitalization, or is a congenital anomaly, cancer, or overdose.

Other important medical events that may not result in death, not be life-threatening, or not require

hospitalization may be considered a serious adverse experience when, based upon appropriate medical judgment, the event may jeopardize the subject/patient and may require medical or surgical intervention to prevent one of the outcomes listed previously.

*Expected adverse events are those adverse events that are listed in the protocol, the Investigator's Brochure (current edition) or in the study informed consent document.*

*Unexpected adverse events are those that:*

- a. are not described in the Investigator's Brochure as far as oxytocin is concerned.
- b. are not anticipated in the study informed consent. This includes adverse events for which the specificity or severity is not consistent with the description in the informed consent.

***Unanticipated problem:*** Per FDA Procedural Guidance for Clinical Investigators, Sponsors, and IRBs (January 2009), A serious problem that has implications for the conduct of the study (requiring a significant and usually safety-related, change in the protocol such as revising inclusion/exclusion criteria or including a new monitoring requirement, informed consent or investigator's brochure).

***Unanticipated problem Reporting:*** Per 21 CFR 312.66, 312.53 (c)(1)(vii), and 56.108(b)(1), should an Unanticipated problem occur during the investigation, the investigator will promptly report all unanticipated problems involving risks to human subjects or others to IRB/FDA.

*The severity or grade of an adverse event may be measured using the following definitions:*

**Mild:** Noticeable to the subject, but does not interfere with subject's expected daily activities, usually does not require additional therapy or intervention, dose reduction, or discontinuation of the study.

**Moderate:** Interferes with the subject's expected daily activities, may require some additional therapy or intervention but does not require discontinuation of the study.

**Severe:** Extremely limits the subject's daily activities and may require discontinuation of study therapy, and/or additional treatment or intervention to resolve.

**Event reporting:** The study will comply with the IRB & FDA reporting requirements and guidelines.

## **8. DATA ANALYSIS/STATISTICAL METHODS**

### **8.1. Sample Size Determination**

Work done by Knutson, Spreckelmeyer and Rademacher, indicate that significant task effects can be observed in the incentive delay task in samples in the range of 15-18 participants [34,35,37,38]. We implemented an fMRI-based power analysis using the fMRIpower software package (fmripower.org). The effect sizes below are expressed in standard deviation units, which is analogous to the Cohen *d* measure. All power calculations are based on ROIs with a p-value threshold of 0.005 for a 1-sided hypothesis test. With 44 subjects, we will have at least 90% power to detect an effect of size 0.77 in the nucleus accumbens, a region known to play a significant role in the processing of rewards [39,40].

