## **3. STUDY DESIGN**

This is a double-blind, placebo-controlled, randomized study of the effects of Syntocinon® on brain activity elicited during the processing of reward. Each participant will be studied twice using fMRI; once self-administering Syntocinon® and once self-administering placebo intranasally approximately 30 minutes prior to being scanned. Participants will be randomly assigned to self-administer either Syntocinon® or placebo first. Scans will be performed on separate days approximately 1-2 weeks apart.

Participants will be evaluated thoroughly at screening for eligibility and will only be entered into the study if they meet all inclusion criteria and none of the exclusion criteria.

88 participants are planned to complete the study (44 controls, 44 AUD). Total duration of the study is expected to be 60 months.

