### 8.2.2. Data Analysis & Anticipated Results.

**Analysis of Primary Objective 1 and 2.** Examine the effects of oxytocin on the modified monetary and social incentive delay tasks.

*Analyses.* We will conduct whole-brain voxel-wise analyses with drug (Syntocinon® or Placebo) as a within-subject factor. We will examine the main effects of drug on reward related BOLD activity across the brain during both anticipation and outcome phases.

*Anticipated Results.* As oxytocin administration has been previously demonstrated to reduce amygdala activity in response to social challenges it is hypothesized that we will see a blunting of amygdala reactivity during the anticipation and attainment of social rewards (particularly for negative social incentives). Oxytocin has also been demonstrated to increase dopaminergic activity within the mesolimbic dopamine system (20) so we may see an enhancement of ventral striatal activity during the anticipation of social rewards; however, as Knutson and collaborators have reported that inducing dopamine release within the ventral striatum by amphetamine can actually reduce the difference in BOLD signal activity seen between the anticipation of reward and the anticipation of null (51), reductions in the BOLD response to anticipation of social reward within the ventral striatum is also possible.

While oxytocin has been predominately noted to affect social processes, there is some data to suggest that oxytocin's effects extend beyond modulating affiliative behaviors. Given this, we hypothesize oxytocin administration will show similar, though perhaps diminished, effects on amygdala and ventral striatal activity in response to the anticipation of monetary rewards as we see in anticipation of social rewards.

**Analysis of Primary Objective 3.** Compare responses to the modified monetary incentive delay task in participants with AUD versus controls.

*Analyses.* We will conduct whole-brain voxel-wise analyses with group (AUD or Control) as a within-subject factor. We will examine the main effects of group on reward related BOLD

activity across the brain during both anticipation and outcome phases.

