### **8.2.3. Potential Pitfalls and Alternative Strategies.**

- We will employ a more sensitive technique, called region-of-interest analyses, to detect potential variation in these conditions. Region-of-interest (ROI) analysis involves looking for changes within selected brain areas, instead of looking for changes across the whole brain. As a relatively smaller number of regions will be examined, the overall number of comparisons will be reduced, resulting in an increase in statistical power. Thus, subtle differences between the conditions can be identified. For our purposes, these ROIs would include the ventral striatum, the amygdala and thalamus.
- Humans are not a homogenous group, thus inter-individual variability may pose some difficulty in discerning effects. Variables such as age can have an impact on task parameters. To address this concern, we will (1) perform regression analyses to determine if there is a relationship between these variables and the contrasts of interest and (2)

perform an analysis of covariance (ANCOVA) to control for these variables. The inclusion of covariates in our analyses will increase overall statistical power as variability will be taken into account. In addition, as some groups have reported certain affiliative characteristics to be related to oxytocin measures, we will also be obtaining measures of attachment and sociability that can be used to help explain some of the variation.

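### The 90% power in Section 8.1 covers only a within-subject ROI contrast; it does not cover the whole-brain primary analyses and is not met for the 44 v 44 group comparison

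*Protocol*

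**What the plan says.** Section 8.1 is the only sample-size justification in the protocol. It says that "All power calculations are based on ROIs with a p-value threshold of 0.005" "for a 1-sided hypothesis test", and concludes: "With 44 subjects, we will have at least 90% power to detect an effect of size 0.77 in the nucleus accumbens". On the scale of the effect it says: "The effect sizes below are expressed in standard deviation units, which is analogous to the Cohen *d* measure". It does not say whether the 44 are one group measured under both drugs or one arm of a two-group comparison. Section 3 plans 88 completers, 44 in each group.

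Section 8.2.2 sets out the analysis of the four primary objectives. For Objectives 1 and 2 (drug effect on social and monetary reward) it says "We will conduct whole-brain voxel-wise analyses with drug" as the factor. For Objective 3 (AUD against controls) it says "We will conduct whole-brain voxel-wise analyses with group (AUD or Control) as a within-subject factor". Objective 4 (drug effect compared between groups) is also whole-brain and voxel-wise.

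ROI analysis enters in Section 8.2.3, on pitfalls and alternative strategies: "We will employ a more sensitive technique, called region-of-interest analyses, to detect potential variation in these conditions". The reason given is that fewer comparisons are made, so power rises. The regions listed are the ventral striatum, amygdala and thalamus.

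**The concern.** A sample-size statement should describe the test that will decide the primary question. Here the power belongs to a single-region test at a per-test threshold of 0.005, while the stated test of every primary objective is a search over the whole brain. Section 8.2.3 itself gives the reason why the two differ: testing fewer regions is more sensitive.

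The second problem lies within the ROI calculation. One figure for 44 subjects is offered for a study with two kinds of contrast. Objectives 1 and 2 compare each person with themselves. Objectives 3 and 4 compare two sets of 44 different people; the label of group as a within-subject factor in 8.2.2 cannot change that. For the same standardised effect, the second kind of contrast has less power.

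At stake is how a null result is read, mainly for the AUD objectives. A reader who carries the 90% from 8.1 to a group or drug-by-group map would credit the study with power that the protocol does not show.

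**Working it through.** **Inputs.** From Section 8.1: d = 0.77 in SD units, one-sided alpha = 0.005, n = 44, stated power at least 90%. From Section 3: 44 completers per group, 88 in all.

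**Formulas.** Power is the probability that a noncentral t variable exceeds the critical value.
- One-sample or paired, n people: df = n − 1, noncentrality = d√n.
- Two groups of n: df = 2n − 2, noncentrality = d√(n/2).

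For Objective 4 the two-group formula applies to each person's oxytocin-minus-placebo difference, with d in SDs of that difference.

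**Step 1: the plan's own figure.**
- Paired, n = 44: noncentrality = 0.77 × √44 = 5.108, df = 43, critical t = 2.695. Power = 99.0%.
- Two groups, 44 v 44: noncentrality = 0.77 × √22 = 3.612, df = 86, critical t = 2.634. Power = 83.3% (85.0% by the normal approximation).

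Neither gives 90% itself. As a lower bound, the statement is true for the paired reading and false for the two-group reading.

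**Step 2: what 90% would need at one-sided 0.005.**

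| Contrast | Detectable d at 90%, n = 44 (per group) | n for 90% at d = 0.77 |
|---|---|---|
| One-sample or paired | 0.605 | 29 |
| Two groups | 0.84 | 52 per group |

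**Step 3: two-sided testing at a total alpha of 0.005.** Paired n = 44: 98.0%. Two groups, 44 v 44: 76.5%.

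**Step 4: illustration for a voxel-wise test.** The protocol gives no whole-brain threshold, so the one-sided per-voxel values below are assumptions. d stays at 0.77.

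| Per-voxel p | Paired, n = 44 | Paired, pooled n = 88 | 44 v 44 |
|---|---|---|---|
| 0.001 | 95.8% | above 99.9% | 66.3% |
| 0.0001 | 83.5% | 99.9% | 40.1% |
| 0.00001 | 62.1% | 99.5% | 20.0% |
| 0.000001 | 38.2% | 97.7% | 8.5% |

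The strictest value is 0.05/50,000, a Bonferroni correction for an assumed 50,000 voxels. Each entry is the power at one voxel with the same d as the ROI. It is not the power of a whole-brain analysis, and cluster-level or small-volume inference would give other values.

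**The case against.** The best defence is that the protocol never claims 90% for the whole-brain maps. Section 8.1 says openly that its calculations are for ROIs. Section 8.2.3 sits under the analysis of the primary endpoint and commits to ROI analyses without condition, and the powered nucleus accumbens lies within the ventral striatum that it lists. The whole-brain threshold may properly be in a SAP. All of this stands, and it is why the missing threshold is not counted as a fault. It does not close the gap: 8.2.2 assigns the whole-brain analysis to each primary objective, and 8.2.3 gives the ROI tests no rank and does not tie them to the powered region or threshold.

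A reader might infer that every objective is underpowered, or that the true power is 38% or 9%. The documents do not support that. Those values rest on assumed single-voxel thresholds. At 0.001 the paired contrast with 44 people still has 95.8%. Section 8.2.2 does not say whether Objectives 1 and 2 pool the groups, and a drug effect pooled over 88 keeps 97.7% even at the strictest value tried.

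A reader might also blame the whole-brain search for the entire group shortfall. It is not the cause of the 83.3%, which arises at the ROI threshold from the type of contrast.

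Nor does failure to reproduce exactly 90% prove an arithmetic error, since 8.1 says at least 90% and does not name the test.

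Finally, one might make a one-sided nucleus accumbens test primary for every objective. That would conflict with 8.2.2, which allows ventral striatal activity to rise or fall under oxytocin and also states hypotheses for the amygdala, the insula and the region it abbreviates as ACING.

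**Conclusion.** The concern holds in a limited form. The 90% in Section 8.1 is for a single-ROI test at one-sided 0.005 and is met only for a one-sample or paired contrast (99.0% at n = 44, d = 0.77). It does not cover the whole-brain analyses that 8.2.2 names for the four primary objectives. It is also not met for the 44 v 44 comparison, where power is 83.3% at the ROI threshold and an effect of about 0.84 SD is needed for 90%.

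The between-group shortfall is the firm number. It assumes a t test on independent groups with 44 completers in each, as Section 3 plans, and d = 0.77 applied to that contrast. A material shortfall for Objectives 1 and 2 is not shown. The whole-brain values are illustrative only. The point should be corrected because it affects how null group findings are read, but it does not invalidate the design.

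**What to change.** In Section 8.1:
- State that the figure of at least 90% at d = 0.77 applies to the within-subject ROI contrast with 44 people.
- Add the between-group figure: about 83% at d = 0.77, or 90% at d of about 0.84, at one-sided 0.005.
- State that no power is claimed for the whole-brain maps.

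In Section 8.2.2:
- Make the ROI analyses promised in 8.2.3 the confirmatory test of each objective, and keep the whole-brain maps as secondary.
- Match the regions to each objective's stated hypotheses. The list in 8.2.3 would need the insula and ACING for Objective 3, and should say how the nucleus accumbens relates to the ventral striatum.
- Test two-sided where the direction is left open, as for the ventral striatal response to oxytocin, and quote the matching power. At a total alpha of 0.005 the paired contrast then has 98.0%; a group contrast, if two-sided, has 76.5%.

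The change is to protocol wording and needs no new data. Its price is that the stated power becomes less favourable for the group objectives and the whole-brain results become exploratory. To keep 90% at d = 0.77 for the group comparison instead would take 52 completers per group, 16 more in all (2 × 52 − 88).

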## 8.2. Analysis of Primary Endpoint

### 8.2.1. fMRI Data Processing.

**Preliminary processing.** All fMRI data will be submitted to an initial series of preprocessing steps (e.g. slice-timing correction, realignment, artifact checks). The functional data acquired for each subject will be coregistered to the structural image collected and finally warped into standardized space using specialized neuroimaging software (e.g. Statistical Parametric Mapping software [SPM8, Wellcome Department of Cognitive Neurology, University College, London, UK]).

**Subject-level analysis.** For each task (for both Syntocinon® and Placebo conditions), a general linear model will be constructed with parameters corresponding to the anticipation and outcome of each type of reward at stake, modeling each session separately. Each stimulus type will be convolved with the hemodynamic response function to assess task-related changes in BOLD signal. Contrasts will be constructed to test for BOLD differences in anticipation activity (anticipation of reward vs null) and outcome activity (outcomes for reward trials versus outcomes for null trials) for each reward type. The statistical maps generated by these analyses will then be slightly smoothed and introduced into second level-analyses.

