### 6.3.2.1. fMRI Tasks

#### Modified Incentive Delay Tasks

The paradigm to be utilized has been used by our laboratory and others to assess functioning of the motivational circuitry in response to monetary rewards (i.e. Monetary Incentive Delay Task, MID) [34-36]. In this adapted paradigm, subjects will be presented with an incentive cue (shape) which signals the potential to either win money, avoid losing money, or whether no money is at stake (See Figure 1). Subjects can earn/avoid losing money during these conditions by pressing a button when a target box, presented after the incentive cue is on the screen. The reaction time used to define the presentation time for the target will be adjusted to ensure a ~66% success rate. Following the target box, subjects will see a feedback screen which will inform them whether they successfully won money or avoided losing money.

**Figure 1. Example of a Single Trial in the MID Task.** Adapted from Knutson, 2000.

**Figure 2. Example of social incentive feedback.** Stimuli taken from Rademacher, 2010.

During some of the trials (i.e. during the Social Incentive Delay Task, SID), the feedback screen will feature a social incentive (i.e. happy faces if they won or successfully avoided losing money or upset faces if they failed to win or lost money). Previous studies performed by Spreckelmeyer and colleagues (Figure 2) have demonstrated that the brain responds differently to social incentives compared to just monetary rewards [37,38]. During the social reward trials, participants will be told that they will be performing this task on behalf of another (a study member) who will be sitting outside of the scanner observing their performance. When the participant successfully 'wins' they will see a picture of that study member's smiling face and if they fail to avoid losing, they will see a picture of that study member's upset face.

Following the scan, the participant will be asked to provide VAS ratings to determine how they felt about the cues from the SID and MID and the feedback screens to examine their affective reactions.

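### The one stated outcome contrast averages successful and failed trials, so it cannot assign an outcome-phase drug effect to attainment or to negative social feedback, as the amygdala prediction requires

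*Protocol*

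**What the plan says.** Section 8.2.1 (Subject-level analysis) builds a general linear model for each task with "parameters corresponding to the anticipation and outcome of each type of reward at stake". It adds that "Each stimulus type will be convolved with the hemodynamic response function". The only outcome contrast it gives is "outcome activity (outcomes for reward trials versus outcomes for null trials) for each reward type".

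Section 6.3.2.1 describes the task. The cue "signals the potential to either win money, avoid losing money, or whether no money is at stake". Target timing is "adjusted to ensure a ~66% success rate". In the social task (SID) the feedback screen shows "happy faces if they won or successfully avoided losing money or upset faces if they failed to win or lost money". A later sentence in the same section says that "if they fail to avoid losing, they will see a picture of that study member's upset face".

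Section 8.2.2, for Objectives 1 and 2, plans to examine "main effects of drug on reward related BOLD activity across the brain during both anticipation and outcome phases". Its anticipated result is that oxytocin will blunt the amygdala response when social rewards are anticipated and when they are attained, with negative social incentives singled out in a parenthesis. The region-of-interest analysis in 8.2.3 narrows the brain areas examined and leaves the contrasts unchanged.

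**The concern.** Attainment occurs only on successful trials, and negative feedback only on failed ones. A contrast built from all outcomes of a stake type puts both into one number. If oxytocin changed the amygdala response at outcome, the planned analysis could report that change but not tie it to either event. The outcome half of the amygdala prediction would then be neither supported nor refuted. Any split made later would be chosen with the data in view.

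**Working it through.** **Inputs.** The only figure from the protocol is the success target of about 66% (6.3.2.1), which makes failures about 34%. It is a design setting, so there is no derived figure to reproduce. Effect sizes below are in arbitrary units and are illustrative.

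**1. What the contrast estimates.** Let Dh, Dm and D0 be the drug effects on successful, failed and null outcomes. With one outcome regressor per stake type:

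pooled drug effect = 0.66 × Dh + 0.34 × Dm − D0

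Assume D0 = 0; the protocol says nothing either way.

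| Pattern | Dh | Dm | Pooled |
|---|---|---|---|
| Successes only | 1 | 0 | 0.66 |
| Failures only | 0 | 1 | 0.34 |
| Equal | 1 | 1 | 1.00 |
| Failures 1.5 times successes | 1 | 1.5 | 0.66 + 0.51 = 1.17 |

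**2. What a pooled result can mean.** A pooled effect of 1.00 is consistent with:
- successes only: 1/0.66 = 1.52
- equal effects: 1.00
- failures only: 1/0.34 = 2.94

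This is one equation in two unknowns, or three if D0 is not zero. At a success rate of 0.60 the success-only and failure-only values are 1/0.60 = 1.67 and 1/0.40 = 2.50. At 0.70 they are 1/0.70 = 1.43 and 1/0.30 = 3.33. The conclusion is the same.

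**3. If separate regressors were fitted but combined equally.** The mix becomes 0.5/0.5. A pooled 1.00 then fits a success-only effect of 1/0.5 = 2.00, an equal effect of 1.00 or a failure-only effect of 2.00. The weights change, and attribution is still lost.

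**4. Whether a split resolves it.** Three patterns give the same pooled effect of −0.224: (Dh, Dm) = (−0.34, 0), (0, −0.66) and (−0.224, −0.224). In a trial-level simulation (assumed: 40 outcome trials, noise SD 1, D0 = 0), separate averages for successes and failures returned about (−0.34, −0.01), (0.00, −0.66) and (−0.22, −0.22). The split tells the three apart.

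**5. What the split costs in precision.** Take trial noise only and assume null trials also succeed 66% of the time. A success-matched contrast has the pooled variance divided by the share of trials used:
- successes: 1/√0.66 = 1.23 times the pooled standard error
- failures: 1/√0.34 = 1.71 times

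If between-subject variance is k times the pooled trial-noise variance (k assumed, and the same for both events), the ratios are √((k + 1/0.66)/(k + 1)) and √((k + 1/0.34)/(k + 1)). That gives 1.12 and 1.40 at k = 1, and 1.06 and 1.22 at k = 3. These are relative precisions, not power figures.

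**The case against.** **Regressor detail belongs in the analysis plan, and the wording about each stimulus type leaves room for separate success and failure terms.** That room exists, and an analysis plan not at hand may use it. But the protocol is not silent here. It fixes an outcome contrast and states an outcome prediction that the contrast cannot resolve. Its parameters are indexed by the reward at stake, so the plain reading is one outcome term per stake type. Success-matched comparisons can be read into the plural wording, but none is named.

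**The 0.66/0.34 weights are not guaranteed.** This stands. They need a single outcome regressor, and the worked effects also need no drug effect on null outcomes. Equal weighting changes the numbers but not the conclusion.

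**Negative social incentives may mean avoid-loss stakes.** It may. If each reward type also means stake type, win and avoid-loss contrasts could be compared. Successes and failures would still be mixed within each.

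**Little depends on it.** Largely true. The objectives in 2.1.1 do not ask for success to be separated from failure. The ventral striatal, monetary, AUD-versus-control and drug-by-group predictions in 8.2.2 concern anticipation.

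Two stronger readings are tempting. A reader might infer that the outcome analysis is invalid or bound to miss real effects. The documents do not support that: the main effect of drug at outcome stays testable, and the pooled contrast is the more precise one for an effect shared by successes and failures. A reader might also infer that 6.3.2.1 gives two conflicting rules for the upset face. The general sentence covers every result. The later one does not say that the face appears only after failing to avoid a loss, so it reads as a shortened example. Confirmation is worth asking for, but a contradiction is not shown.

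**Conclusion.** The point holds in limited form. As written, the outcome contrast yields an average over successes and failures. It cannot attribute a drug effect to attainment or to negative social feedback, which the outcome half of the amygdala prediction for Objectives 1 and 2 needs. Outcome-phase group and drug-by-group results would carry the same limit, although no stated prediction turns on it.

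The loss is one of attribution: the same pooled result fits a success-only effect of 1.52 or a failure-only effect of 2.94. Those figures assume one outcome regressor per stake type, success at 66% and no drug effect on null outcomes. Reading the average as a drug effect also assumes similar success rates under drug and placebo, which the timing adjustment aims at. Anticipation contrasts are untouched.

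**What to change.** In 8.2.1:
- Model successful and failed outcomes separately for each stake type (win, avoid-loss, null) and each task.
- Define attainment as successful reward outcomes versus null outcomes, matched on success where null trials are scored.
- Define negative social feedback as SID outcomes that show the upset face versus null outcomes.
- Add a direct failed-versus-successful comparison for the claim that negative incentives are affected most.
- Keep the pooled contrast alongside.

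In 8.2.2, state whether negative social incentives means upset-face feedback or avoid-loss stakes. If it means avoid-loss stakes, name the avoid-loss versus win comparison. In 6.3.2.1, confirm which failed trials show the upset face.

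The change is to model specification and wording. It uses trial results that the task already generates and needs no new participants or scans. The downside is noisier split estimates: standard errors roughly 1.2 times pooled for successes and 1.7 times for failures if trial noise alone counted and null success were also 66%, and less once between-subject variance is included.
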